4.2.2.1 MGC018

MGC018 will be administered by IV infusion at a dose of 2.0 mg/kg on Day 1 of each 28-day cycle until completion of cycle 8, unacceptable toxicity, or loss of clinical benefit as determined by the investigator after an integrated assessment of radiographic and biochemical data, local biopsy results (if available), and clinical status (see Section 3.1.1 for details). For subjects weighing ≥ 100 kg the doses will be based on 100 kg for these subjects. To decrease the frequency and severity of palmar-plantar erythrodysesthesia (PPE) and effusions, prednisone 40 mg will be given twice daily for three days of each cycle starting the evening after each infusion for a total of 6 doses. In addition, patients will be provided with a strong or moderate-strength topical steroid cream to be applied as prescribed to the hands and soles prophylactically for the first 12 weeks of therapy.

Administration of MGC018 will be performed in a monitored setting where there is immediate access to trained personnel and adequate equipment and medicine to manage potentially serious reactions. For anaphylaxis precautions, see Appendix 3. MGC018 infusions will be administered per the instructions outlined in Table 3.

Table 3. Administration of first and subsequent MGC018 infusions

| Study Drug | First Infusion | Subsequent Infusions |
|-----------------|---|--|
| MGC018 infusion | 
Premedication with acetaminophen (650mg to 1000 mg), diphenhydramine 50 mg PO or IV, famotidine 40 mg PO or 20 mg IV, and corticosteroid (e.g | 
If the patient experienced an infusion-related reaction (IRR) with any previous infusion, additional premedication may also be considered. |

| | | |
|---|---|---|
| | 
dexamethasone 4 mg IV or equivalent)
 
 • Vital signs (pulse rate, respiratory rate, blood pressure, and temperature) should be measured within 60 minutes prior to the infusion. • MGC018 should be infused over 60 minutes. Up to 10 additional minutes of infusion time is permitted to allow for flushing the IV line. • If clinically indicated, vital signs should be measured every 15 (\pm 5) minutes during the infusion. • Patients should be informed about the possibility of delayed post-infusion symptoms and instructed to contact their study physician if they develop such symptoms. | 
 • Vital signs should be measured within 60 minutes prior to the infusion. • MGC018 should be infused over 60 minutes (\pm 10 minutes) if the previous infusion was tolerated without an IRR, or 60 (\pm 15) minutes if the patient experienced an IRR with the previous infusion. • If clinically indicated, vital signs should be measured during the infusion and at 30 (\pm 10) minutes after the infusion. |
| Observation period after infusion of MGC018 | 
 • After the infusion of MGC018, the patient begins a 60-minute observation period. • Vital signs should be recorded at 30 \pm 10 minutes after the infusion of MGC018. • Patients will be informed about the possibility of delayed post-infusion symptoms and instructed to contact their study physician if they develop such symptoms. | 
 • If the patient tolerated the previous MGC018 infusion well without infusion-associated adverse events, no observation period is needed. • If the patient experienced infusion-associated adverse events in the previous infusion, an observation period of 60 minutes should occur. • If clinically indicated, vital signs should be recorded at 30 (\pm 10) minutes after the infusion of MGC018. |

Refer to the pharmacy manual for detailed instructions on drug preparation, storage, and administration.

4.2.3 **Dose modification and management of adverse events**

4.2.3.1 **General notes regarding dose modifications & delays**

Reasons for dose delays, supportive measures taken, and subsequent outcome will be documented in the patient's chart and recorded on the eCRF. The severity of adverse events will be graded according to the NCI CTCAE v5.0 grading system.

- When several toxicities with different grades of severity occur at the same time, appropriate action should be made according to the highest grade observed.
- If, in the opinion of the investigator, a toxicity is considered to be due solely to MGC018 and is of sufficient grade to warrant treatment delay, therapy should be delayed and omitted until resolution of toxicity.
- If, in the opinion of the investigator, a toxicity attributed to MGC018 is of sufficient grade to warrant permanent discontinuation of therapy, therapy should be permanently discontinued.

For patients who require a dose-reduction, the first reduction would be to 1.5 mg/kg every 28 days with a second reduction to 1.0 mg/kg every 28 days, as needed (**Table 4**).

Table 4. Dose levels of MGC018

| Dose levels | MGC018 |
|-------------------------|---------------|
| Level 1 (starting dose) | 2.0 mg/kg Q4W |
| Level -1 | 1.5 mg/kg Q4W |
| Level -2 | 1.0 mg/kg Q4W |

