4.2.3.2 Guidelines for management of suspected MGC018-related toxicities

Criteria for treatment modification and guidelines for the management of toxicities are summarized below. Generally, temporary suspension of MGC018 must occur if a patient experiences a serious adverse event or a grade 3 or 4 non-serious adverse event assessed by the investigator as related to MGC018. If the event resolves to grade ≤ 1 , MGC018 may be restarted at the same dose level. If MGC018 is delayed due to toxicity for > 8 weeks beyond when the next dose should have been given, the patient must be permanently discontinued from MGC018.

PULMONARY EVENTS

Immune-mediated pulmonary events are a potential risk with MGC018. Patients will be assessed for pulmonary signs and symptoms throughout the study and will have computed tomography (CT) scans of the chest performed at every tumor assessment.

All pulmonary events should be thoroughly evaluated for other commonly reported etiologies such as pneumonia or other infection, lymphangitic carcinomatosis, pulmonary embolism, heart failure, chronic obstructive pulmonary disease, or pulmonary hypertension. Management guidelines for pulmonary events are provided in Table 5.

Table 5. Management Guidelines for Pneumonitis

| Event | Management |
|--------------|---|
| Grade 1 | 
 • Continue MGC018 and monitor closely. • Re-evaluate on serial imaging. • No specific therapy required |
| Grade 2 | 
 • Hold MGC018 • Consider treatment with corticosteroids equivalent to 1–2 mg/kg/day oral prednisone or equivalent divided twice daily • Taper corticosteroids over 4 weeks or as clinically indicated • Resume MGC018 administration at next scheduled dose if pneumonitis resolves to grade 1 or baseline within 5 days with or without treatment. On resuming MGC018, reduce dose by one dose level. • Discontinue MGC018 after second occurrence |
| Grade 3 or 4 | 
 • Permanently discontinue MGC018 • Hospitalize • Referral for pulmonary consult with diagnostic evaluation with chest X-ray and CT scan. • Initiate treatment with IV corticosteroids, suggest methylprednisolone at 2 to 4 mg/kg/day divided twice daily. Higher doses may be used in consultation with the sponsor's medical monitor. • If event does not improve within 3 to 5 days after initiating corticosteroids, consider adding an immunomodulatory agent. |

HEPATIC EVENTS

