For palmar-plantar erythrodysesthesia, hold MGC018 until toxicity resolves to \leq grade 1. MGC018 may be resumed with MGC018 decrease of one dose level. Discontinue MGC018 if patient does not recover to \leq grade 1 within 28 days.

Table 9. Management Guidelines for Dermatologic Events

| Event | Management |
|-------|------------|
|-------|------------|

| | |
|-----------------------------|---|
| Dermatologic event, Grade 1 | 
 • For dry skin, consider application of moisturizers as needed to affected area • Symptomatic treatment with low dose topical corticosteroids (betamethasone 0.1% or hydrocortisone 1%) or antihistamines • Persistent grade 1 or 2 rash should be managed with higher dose topical corticosteroids and/or oral prednisone (1 to 2 mg/kg/day) if there is not improvement with topical therapies or the rash is associated with other dermal toxicities such as pruritis. • Evaluate for use of concomitant medications and herbal supplements that may exacerbate skin toxicity. |
| Dermatologic event, Grade 2 | 
 • Treat as grade 1 • No dose reduction required after first occurrence • On resuming MGC018, reduce dose by one dose level after second and third occurrences • Discontinue MGC018 after fourth occurrence |
| Dermatologic event, Grade 3 | 
 • Hold MGC018 • Initiate oral corticosteroids (oral prednisone 1 to 2 mg/kg/day) • Evaluate participant use of concomitant medications and herbal supplements that may exacerbate skin toxicity • Consider obtaining skin biopsy if SJS or TEN is suspected. If possible, refer to specialized care center for clinical management. Cyclosporine and/or IV immunoglobulin may be considered for management of SJS or TEN. • Resume MGC018 at next scheduled dose if: • Skin toxicity resolves to \leq grade 1 or baseline within 21 days with maximal supportive care • Discontinue study drugs if skin toxicity does not resolve to \leq grade 1 or baseline within 21 days, or for any grade SJS or TEN of any duration. • On resuming MGC018, reduce dose by one dose level after first and second occurrences • Discontinue MGC018 after third occurrence |

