| Blepharitis, Grade 2 | 
 Hold MGC018 Consider topical/ocular corticosteroids, antihistamine, artificial tears Resume MGC018 if resolved to \leq grade 1 within 28 days and discontinue MGC018 if symptoms last > 28 days On resuming MGC018, if symptoms lasted > 14 days, reduce dose by one dose level |
| Blepharitis, Grade 3 | 
 Hold MGC018 Consider referral to ophthalmologist. Consider topical/ocular and/or systemic corticosteroids Resume MGC018 if resolved to \leq grade 1 within 28 days and discontinue MGC018 if symptoms last > 28 days On resuming MGC018, reduce dose by one dose level |
| Blepharitis, Grade 4 | 
 Permanently discontinue MGC018 Consult ophthalmology within 24 hours Treat as for grade 3 and as appropriate for life-threatening symptoms |

HEMATOLOGIC EVENTS

Blood counts should be monitored to determine if dose modification is needed. Consider monitoring CBC bi-weekly or weekly based on the participant's medical history and incidence of myelosuppressive AE's during study drug administration.

Blood counts will be performed in case of fever (a measured temperature of 100.4 F or greater) or evidence of infection. Neutropenic complications should be managed promptly with antibiotic support and use of G-CSF according to current ASCO guidelines for use of white blood cell growth factors.

Consider transfusion of platelets for thrombocytopenia. Use of anticoagulants and platelet inhibitors should be held until thrombocytopenia resolves.

Anemia should be evaluated and treated for other underlying etiology e.g. iron or vitamin B12 deficiency, bleeding, and renal insufficiency. Consider transfusion of red blood cells or whole blood for

anemia. Caution is recommended in patients with \geq grade 2 anemia, with appropriate measures taken as clinically indicated. Patients will be supported appropriately by the treating physician.

No specific treatment or drug holds are required for lymphopenia, regardless of CTCAE grade, unless associated with opportunistic infection. If the patient develops an opportunistic infection with concurrent lymphopenia, MGC018 should be delayed until resolution of lymphopenia and the opportunistic infection

Management guidelines for hematologic events are provided in Table 13.

Table 13. Management Guidelines for Hematologic Events

| Event | Management |
|------------------------------|--|

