| Neutropenia, Grade 1 or 2 | 
 • No specific therapy required • MGC018 should not be given to participants with neutrophil counts ≤ 1500 cells/mm³ • Consider dose reduction of MGC018 |
| Neutropenia, Grade 3 | 
 • Hold MGC018 until recovery to \leq grade 1 • Monitor neutrophil counts weekly until recovery to \leq grade 1 • Discontinue MGC018 if not recovered to \leq grade 1, within 21 days • Restart MGC018 if recovered to \leq grade 1 within 21 days. • On resuming MGC018, reduce dose by one dose level after first and second occurrences • Discontinue MGC018 after third occurrence |
| Neutropenia, Grade 4 | 
 • Hold MGC018 until recovery to \leq grade 1 • Monitor neutrophil counts weekly until recovery to \leq grade 1 • Discontinue MGC018 if not recovered to \leq grade 1, within 21 days • Restart MGC018 at one or two level dose reduction if recovered to \leq grade 1 within 21 days. • On resuming MGC018 reduce dose by two dose levels after first occurrence • Discontinue MGC018 after second occurrence |
| Thrombocytopenia, Grade 1 | 
 • No specific therapy required • Consider dose reduction of MGC018 |

| | |
|-----------------------------------|--|
| Thrombocytopenia, Grade 2 or 3 | 
 • Hold MGC018 until recovery to \leq grade 1 • Monitor platelet counts weekly until recovery to \leq grade 1 • Restart MGC018 with one level dose reduction if recovered to \leq grade 1 • Reduce dose by one dose level on resumption after second and third occurrences • Discontinue MGC018 after fourth occurrence • Discontinue MGC018 if not recovered to \leq grade 1 within 21 days. |
| Thrombocytopenia, Grade 4 | 
 • Hold MGC018 until recovery to \leq grade 1 • Monitor platelet counts weekly until recovery to \leq grade 1 • Restart MGC018 with one or two level dose reduction if recovered to \leq grade 1 • Discontinue MGC018 if not recovered to \leq grade 1 within 21 days. • On resuming MGC018 reduce dose by two dose levels after first occurrence • Discontinue MGC018 after second occurrence |
| Anemia, Grade 1 | 
 • No specific therapy required |
| Anemia, Grade 2 | 
 • Consider iron replacement therapy, erythropoiesis stimulating agent |

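### Section 4.2.3.1 ranks concurrent toxicities by grade, but MGC018 actions are not ordered by grade across events, so a dose reduction required by a lower-grade event can be lost

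*Combined protocol and SAP*

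**What the plan says.** The first bullet of Section 4.2.3.1 covers coinciding toxicities of different grades: "appropriate action should be made according to the highest grade observed". The next two bullets concern a toxicity that the investigator judges severe enough for delay (if due to MGC018 alone) or for stopping; the latter applies where "a toxicity attributed to MGC018 is of sufficient grade to warrant permanent discontinuation of therapy". The dose steps follow: "the first reduction would be to 1.5 mg/kg every 28 days with a second reduction to 1.0 mg/kg every 28 days" (Table 4).

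Section 4.2.3.2 then gives a general rule and event-specific rules:

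- **General rule.** For events judged related, "temporary suspension of MGC018 must occur if a patient experiences a serious adverse event or a grade 3 or 4 non-serious adverse event". After resolution to grade 1 or better, restart at an unchanged dose level is allowed.
- **Grade 2 pneumonitis (Table 5).** Hold. If it resolves in time, "On resuming MGC018, reduce dose by one dose level".
- **Grade 2 or 3 thrombocytopenia (Table 13).** Hold until grade 1 or better. One line says "Restart MGC018 with one level dose reduction if recovered to" that grade; another attaches a one-level reduction to the second and third occurrences.
- **Grade 3 anemia (Table 13).** A hold is to be considered. A reduction is required only from the second event.
- **Lymphopenia (text before Table 13).** "No specific treatment or drug holds are required for lymphopenia, regardless of CTCAE grade, unless associated with opportunistic infection".
- **Palmar-plantar erythrodysesthesia (PPE; text before Table 9).** Hold until grade 1 or better, then "MGC018 may be resumed with MGC018 decrease of one dose level". The rule names no starting grade.

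**The concern.** Letting the highest grade decide works when actions become stricter as grade rises. Within most single-event tables they do. Across events they do not: some grade 2 events carry firm instructions, while some grade 3 or 4 findings carry weak ones. A site that applies the bullet as written could take its instruction from the higher-grade but less consequential event.

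At stake is the dose at the next infusion. Pneumonitis and myelosuppression are both listed risks of MGC018 in Section 5.1.1. Section 3.1.3 names four sites and allows more, so different readings would also make dosing inconsistent in a trial whose secondary objectives include the safety profile.

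**Working it through.** The plan gives no figure for this point. The check is a comparison of rules, followed by dose arithmetic from Table 4.

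**Step 1. Required action on MGC018, event by event**

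| Event | Hold required? | Reduction required at first occurrence? |
|---|---|---|
| Pneumonitis, grade 2 | Yes | Yes, one level |
| Thrombocytopenia, grade 2 | Yes | Supported by the restart line, but the row is ambiguous |
| Anemia, grade 3 | Optional in its row; the general rule supplies a hold if related | No |
| Lymphopenia, grade 3–4, no opportunistic infection | No | No |

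**Step 2. Apply the first bullet literally**

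- *Grade 2 pneumonitis with a first grade 3 anemia.* The highest grade is 3, so the anemia row decides. The hold is optional there, or comes from the general rule if the anemia is related. Neither source requires a reduction, and the general rule allows the same level at restart. Pneumonitis alone would have required one level lower.
- *Grade 2 pneumonitis with grade 3–4 lymphopenia.* The lymphopenia text decides, and it requires neither a hold nor a reduction.
- *Grade 2 thrombocytopenia with grade 3–4 lymphopenia.* The conflict over the hold is the same. Platelets and lymphocytes come from the same hematology panel (Section 4.4.6), so the pair would be seen together. The reduction is less certain: reducing at the first, second and third occurrences needs three steps, and Table 4 has two levels below the starting dose.

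**Step 3. Look for a precedence rule**

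Nothing in Sections 4.2.3.1 or 4.2.3.2 says that the strictest action, or a reduction required by the lower-grade event, overrides the first bullet. The second and third bullets address delay and discontinuation, not reduction. Section 4.4 allows dosing only when the clinical and laboratory findings are acceptable; that governs whether to dose, not at what level.

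**Step 4. Size of a lost one-level reduction (2.0, 1.5, 1.0 mg/kg)**

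- From the starting dose: (2.0 − 1.5) / 1.5 = 33% above the level the row calls for.
- From level −1, reached for some other toxicity: (1.5 − 1.0) / 1.0 = 50% above.

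**Step 5. Design figures**

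The exact two-stage calculation (9 then 8 patients, 3 or more responses in 17) gives a type I error of 0.0466 and power of 0.8122. These match the stated 4.7% and 81.2%, and no dosing rule enters either.

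**The case against.** The strongest reply is that the rules do not collide. The lymphopenia text says only that lymphopenia does not itself call for a hold; it does not tell a site to dose through pneumonitis. The anemia row permits a hold and does not forbid a reduction. A site can obey these and the grade 2 row together. The first bullet is a general note, asks for appropriate action, and is probably meant to stop sites acting on the milder event. The event rows carry no exception for coincident toxicities.

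Much of this stands. A reader might infer that the protocol directs full dosing through pneumonitis or low platelets. It does not: the event rows, the second and third bullets, the general suspension rule and the pre-dose check in Section 4.4 together make a missed hold unlikely. A reader might also pair grade 2 myocarditis (permanent stop) with grade 3 neutropenia (resumption allowed). There the third bullet and the intolerable-toxicity criterion in Section 4.5.1 support stopping. PPE should not be counted as a grade 2 conflict, since its rule is not grade-specific. Effusions are left out because Section 4.2.3.2 separately tells sites to consider a delay or reduction.

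What does not stand is that these provisions also protect the reduction. They back up the hold or the stop. The reduction depends on the lower-grade event's own row, which the first bullet can be read to displace, and the general rule allows restart at the same level.

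**Conclusion.** The point holds as a minor correction to a safety rule, worth considering at the next amendment. The clearest case is grade 2 pneumonitis with a first grade 3 anemia, or with grade 3–4 lymphopenia without opportunistic infection. Thrombocytopenia with lymphopenia illustrates the conflict over the hold; its first-occurrence reduction is less clear.

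The size is one dose level: 33% above the required dose from 2.0 mg/kg, or 50% above from 1.5 mg/kg. This assumes that a site lets the first bullet override the lower-grade event's row, and that Table 4 and the event tables govern reductions. (Section 4.2.2 has a sentence ruling out dose modification, which does not fit with them.)

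A reader might infer a number of patients at risk among the 17, or a bias in the efficacy result. The documents give no incidence for these pairs, so the first cannot be derived. The second is not supported: the ORR definition, sample size and error rates do not depend on this bullet.

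**What to change.** Replace the first bullet of Section 4.2.3.1 with:

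*When several toxicities occur at the same time, manage each according to its own table or text, and apply to MGC018 the most restrictive action required by any of them (permanent discontinuation > hold with dose reduction > hold > continue); where more than one dose reduction applies, use the larger; MGC018 resumes only when the resumption criteria of every concurrent event are met.*

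The last clause matters because recovery windows differ: 5 days for grade 2 pneumonitis, 21 for thrombocytopenia, 28 for PPE. Actions that a table only asks the investigator to consider remain a matter of judgment. Clarifying whether the grade 2–3 thrombocytopenia row intends a reduction at first occurrence would remove the ambiguity noted above.

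The cost is a short wording change in an amendment, with no new visits or data. The downside is slightly more holds or reductions at sites that would have followed grade alone, all of them already called for by the individual event rules.

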4.2.3.2 Guidelines for management of suspected MGC018-related toxicities

Criteria for treatment modification and guidelines for the management of toxicities are summarized below. Generally, temporary suspension of MGC018 must occur if a patient experiences a serious adverse event or a grade 3 or 4 non-serious adverse event assessed by the investigator as related to MGC018. If the event resolves to grade ≤ 1 , MGC018 may be restarted at the same dose level. If MGC018 is delayed due to toxicity for > 8 weeks beyond when the next dose should have been given, the patient must be permanently discontinued from MGC018.

PULMONARY EVENTS

Immune-mediated pulmonary events are a potential risk with MGC018. Patients will be assessed for pulmonary signs and symptoms throughout the study and will have computed tomography (CT) scans of the chest performed at every tumor assessment.

All pulmonary events should be thoroughly evaluated for other commonly reported etiologies such as pneumonia or other infection, lymphangitic carcinomatosis, pulmonary embolism, heart failure, chronic obstructive pulmonary disease, or pulmonary hypertension. Management guidelines for pulmonary events are provided in Table 5.

Table 5. Management Guidelines for Pneumonitis

| Event | Management |
|--------------|---|
| Grade 1 | 
 • Continue MGC018 and monitor closely. • Re-evaluate on serial imaging. • No specific therapy required |
| Grade 2 | 
 • Hold MGC018 • Consider treatment with corticosteroids equivalent to 1–2 mg/kg/day oral prednisone or equivalent divided twice daily • Taper corticosteroids over 4 weeks or as clinically indicated • Resume MGC018 administration at next scheduled dose if pneumonitis resolves to grade 1 or baseline within 5 days with or without treatment. On resuming MGC018, reduce dose by one dose level. • Discontinue MGC018 after second occurrence |
| Grade 3 or 4 | 
 • Permanently discontinue MGC018 • Hospitalize • Referral for pulmonary consult with diagnostic evaluation with chest X-ray and CT scan. • Initiate treatment with IV corticosteroids, suggest methylprednisolone at 2 to 4 mg/kg/day divided twice daily. Higher doses may be used in consultation with the sponsor's medical monitor. • If event does not improve within 3 to 5 days after initiating corticosteroids, consider adding an immunomodulatory agent. |

HEPATIC EVENTS

Immune-mediated hepatic events are a potential risk with MGC018.

Immune-related hepatitis has been associated with the administration of MGC018.-Eligible patients must have adequate liver function, as manifested by measurements of total bilirubin and hepatic transaminases, and liver function will be monitored throughout study treatment.

Patients with right upper-quadrant abdominal pain and/or unexplained nausea or vomiting should have liver function tests (LFTs) performed immediately and reviewed before administration of the next dose of study drug.

For patients with elevated LFTs, concurrent medication, viral hepatitis, and toxic or neoplastic etiologies should be considered and addressed, as appropriate.

Table 6. Management Guidelines for Elevations in Transaminases

| Event | Management |
|-------|------------|
|-------|------------|

| | |
|---------|--|
| Grade 1 | 
 • Continue MGC018. • No specific therapy required • Monitor LFTs until values resolve to within normal limits or to baseline values. |
| Grade 2 | 
 • Rule out viral and other etiologies • Consider imaging such as ultrasound, or CT scan • Hold MGC018 • Consider starting oral prednisone 1 mg/kg per day • If improvement to grade 1 or baseline does not occur within 72 hours with oral steroids, consider IV steroids (i.e methylprednisolone 1-2 mg/kg/day divided twice daily) • Resume MGC018 at next scheduled dose if no more than one dose of MGC018 was missed • If improvement to grade 1 or baseline does not occur within 21 days, discontinue MGC018 • No dose reduction required after first occurrence • On resuming MGC018, reduce dose by one dose level after second and third occurrences • Discontinue MGC018 after fourth occurrence |
| Grade 3 | 
 • Hold MGC018 • Begin IV steroids methylprednisolone 2 mg/kg/day divided twice daily and if no response within 3 to 5 days, consider adding additional immune suppression therapy (e.g. mycophenolate). • Monitor liver functions tests at least twice weekly (or more frequently as clinically appropriate) until transaminases have returned to grade 1. • For elevations in transaminases >8 x ULN, permanently discontinue MGC018. • If elevation does not improve to grade 2 within 10 days and to grade 1 within 21 days, discontinue MGC018. • Resume MGC018 if following conditions are met: 
 ○ Lab elevations improve to grade 2 within 10 days and to grade 1 within 21 days ○ Steroids have been tapered to ≤10 mg per day or prednisone or equivalent ○ On resuming MGC018, LFT's will be evaluated at least once per week for 3 consecutive weeks • On resuming MGC018, reduce dose by one dose level after first and second occurrences |

| | |
|---------|---|
| | 
 Discontinue MGC018 after third occurrence |
| Grade 4 | 
 Treat as grade 3 as above On resuming MGC018 reduce dose by two dose levels after first occurrence Discontinue MGC018 after second occurrence |

Table 7. Management Guidelines for Elevations in Total Bilirubin

| Event | Management |
|---------|--|
| Grade 1 | 
 Continue MGC018 No specific therapy required |
| Grade 2 | 
 Hold MGC018 until improvement to \leq grade 1 Rule out viral and other etiologies Consider imaging studies such as ultrasound or CT scan, and liver biopsy to ascertain etiology of liver dysfunction Consider oral prednisone 1 mg/kg If improvement to \leq grade 1 does not occur within 21 days, discontinue MGC018 and begin oral steroids No dose reduction required after first occurrence On resuming MGC018, reduce dose by one dose level after second and third occurrences Discontinue MGC018 after fourth occurrence |
| Grade 3 | 
 Hold MGC018 For elevations in total bilirubin $>5 \times$ ULN 
 Permanently discontinue MGC018 and initiate IV steroids, i.e methylprednisolone 2 mg/kg/day divided twice daily If no response to corticosteroids within 3 to 5 days, consider adding additional immune suppression therapy (e.g. mycophenolate) Monitor liver function testing at least twice weekly (or more frequently as clinically appropriate) until total bilirubin has returned to grade 1 or baseline For elevation in total bilirubin >3 but ≤ 5 times ULN 
 Begin IV steroids, i.e methylprednisolone at 2 mg/kg/day divided twice daily. Consider additional immune suppression as above if no response to corticosteroids within 3 to 5 days |

| | |
|---------|---|
| | 
 ○ Monitor liver function testing at least twice weekly (or more frequently as clinically appropriate) until total bilirubin has returned to grade 1 or baseline. • Resume MGC018 if: 
 ○ Total bilirubin elevations improve to \leq grade 2 within 7 days and improve to \leq grade 1 or baseline within 21 days ○ Steroids have been tapered to ≤ 10 mg per day of prednisone or equivalent ○ On resuming MGC018, monitor liver function testing at least once per week for 3 consecutive weeks • On resuming MGC018, reduce dose by one dose level after first and second occurrences • Discontinue MGC018 after third occurrence |
| Grade 4 | 
 • Treat as grade 3 elevation • On resuming MGC018 reduce dose by two dose levels after first occurrence • Discontinue MGC018 after second occurrence |

GASTROINTESTINAL EVENTS

Immune-mediated colitis has been associated with administration of MGC018.

Management guidelines for diarrhea or colitis are provided in Table 8.

All events of diarrhea or colitis should be thoroughly evaluated for other more common etiologies. For events of significant duration or magnitude or associated with signs of systemic inflammation or acute-phase reactants (e.g., increased C-reactive protein, platelet count, or bandemia): Perform sigmoidoscopy (or colonoscopy, if appropriate) with colonic biopsy.

Table 8. Management Guidelines for Gastrointestinal Events (Diarrhea or Colitis)

| Event | Management |
|------------------------------|---|
| Diarrhea or colitis, Grade 1 | 
 • Continue MGC018 • Initiate symptomatic treatment. • Closely monitor the diarrhea until resolution |
| Diarrhea or colitis, Grade 2 | 
 • Hold MGC018 • On resolution to grade 1 or baseline, resume MGC018 without dose reduction • Increase frequency of monitoring until resolution • Initiate symptomatic treatment. |

| | |
|------------------------------|--|
| | 
 ○ Loperamide and or diphenoxylate/atropine ○ Low dose steroids, if clinically indicated ○ Consider management or prolonged grade 2 event lasting more than 5 to 7 days or relapsed diarrhea as grade 3 diarrhea (below) |
| Diarrhea or colitis, Grade 3 | 
 ● Hold MGC018. Hospitalize patient promptly for further evaluation and management including the following: 
 ○ Bowel rest ○ IV fluid with close monitoring of fluid and electrolyte status ○ Consider imaging to rule out bowel obstruction or perforation ○ Consideration of colonoscopy as appropriate ○ Empiric immune suppression with IV corticosteroids using methylprednisolone at 2 mg/kg/day (or equivalent) divided twice daily. As tolerated steroids may be converted to oral corticosteroids and tapered as appropriate guided by patient's clinical status ○ For patients who do not respond to corticosteroids, additional immunosuppression with anti-TNF alpha antibodies (i.e infliximab) should be considered. ● If it is determined there is no colitis and an alternative cause of diarrhea is found, consider restarting MGC018 if diarrhea resolves to \leq grade 1 within 21 days ● On resuming MGC018, reduce dose by one dose level after first and second occurrences ● Discontinue MGC018 after third occurrence |
| Diarrhea or colitis, Grade 4 | 
 ● Treat as grade 3 ● On resuming MGC018 reduce dose by two dose levels after first occurrence ● Discontinue MGC018 after second occurrence |

DERMATOLOGIC EVENTS

Immune-related dermatologic events are a potential risk with MGC018. Management guidelines for dermatologic events are provided in Table 9. Patients should limit sun exposure and apply broad spectrum sunscreen to exposed skin when outdoors.

For palmar-plantar erythrodysesthesia, hold MGC018 until toxicity resolves to \leq grade 1. MGC018 may be resumed with MGC018 decrease of one dose level. Discontinue MGC018 if patient does not recover to \leq grade 1 within 28 days.

Table 9. Management Guidelines for Dermatologic Events

| Event | Management |
|-------|------------|
|-------|------------|

| | |
|-----------------------------|---|
| Dermatologic event, Grade 1 | 
 • For dry skin, consider application of moisturizers as needed to affected area • Symptomatic treatment with low dose topical corticosteroids (betamethasone 0.1% or hydrocortisone 1%) or antihistamines • Persistent grade 1 or 2 rash should be managed with higher dose topical corticosteroids and/or oral prednisone (1 to 2 mg/kg/day) if there is not improvement with topical therapies or the rash is associated with other dermal toxicities such as pruritis. • Evaluate for use of concomitant medications and herbal supplements that may exacerbate skin toxicity. |
| Dermatologic event, Grade 2 | 
 • Treat as grade 1 • No dose reduction required after first occurrence • On resuming MGC018, reduce dose by one dose level after second and third occurrences • Discontinue MGC018 after fourth occurrence |
| Dermatologic event, Grade 3 | 
 • Hold MGC018 • Initiate oral corticosteroids (oral prednisone 1 to 2 mg/kg/day) • Evaluate participant use of concomitant medications and herbal supplements that may exacerbate skin toxicity • Consider obtaining skin biopsy if SJS or TEN is suspected. If possible, refer to specialized care center for clinical management. Cyclosporine and/or IV immunoglobulin may be considered for management of SJS or TEN. • Resume MGC018 at next scheduled dose if: • Skin toxicity resolves to \leq grade 1 or baseline within 21 days with maximal supportive care • Discontinue study drugs if skin toxicity does not resolve to \leq grade 1 or baseline within 21 days, or for any grade SJS or TEN of any duration. • On resuming MGC018, reduce dose by one dose level after first and second occurrences • Discontinue MGC018 after third occurrence |
| Dermatologic event, Grade 4 | 
 • Initiate oral corticosteroids (oral prednisone 1 to 2 mg/kg/day) • Evaluate patient for use of concomitant medications or herbal supplements that may exacerbate skin toxicity • Consider obtaining a skin biopsy if possible diagnosis of SJS or TEN. If possible, refer to specialized care center for clinical management. Cyclosporine and/or IV immunoglobulin may be considered for management of SJS or TEN. |

| | |
|--|---|
| | 
 • Consideration should be given to start IV corticosteroids (methylprednisolone 1 to 2 mg/kg/day) for grade 4 dermatologic toxicities with tapering on resolution to <grade 2 over 30 days. • If SJS or TEN are confirmed, permanently discontinue MGC018 • On resuming MGC018 reduce dose by two dose levels after first occurrence • Discontinue MGC018 after second occurrence |
|--|---|

SJS=Stevens-Johnson Syndrome, TEN=toxic epidermal necrolysis

RENAL EVENTS

Immune-related nephritis is a potential risk with MGC018. Eligible patients must have adequate renal function. Renal function, including serum creatinine, should be monitored throughout study treatment. Patients with abnormal renal function should be evaluated and treated for other more common etiologies (including prerenal and postrenal causes, and concomitant medications such as non-steroidal anti-inflammatory drugs).

Patients with signs and symptoms of nephritis, in the absence of an identified alternate etiology, should be treated according to the guidelines in Table 10.

Table 10. Management Guidelines for Nephritis

| Event | Management |
|--------------------|---|
| Nephritis, Grade 1 | 
 • Continue MGC018 • No specific therapy required • Close monitoring of renal function |
| Nephritis, Grade 2 | 
 • Hold MGC018 • Consider nephrology consultation and renal biopsy to confirm interstitial nephritis. • Consider initiating treatment with corticosteroids equivalent to 1–2 mg/kg/day oral prednisone per day, dose divided twice daily. • Taper corticosteroids over 4 weeks or as clinically indicated. • Resume MGC018 at next scheduled dose if nephritis resolves to \leq grade 1 within 21 days with or without treatment • No dose reduction required after first occurrence • On resuming MGC018, reduce dose by one dose level after second and third occurrences • Discontinue MGC018 after fourth occurrence |

| | |
|--------------------|--|
| Nephritis, Grade 3 | 
 • Consider hospitalization, nephrology consultation, and renal biopsy to confirm interstitial nephritis. • Initiate treatment with corticosteroids equivalent to 2–4 mg/kg/day IV methylprednisolone divided twice daily. Taper corticosteroids over 4 weeks or as clinically indicated. • On resuming MGC018, reduce dose by one dose level after first and second occurrences • Discontinue MGC018 after third occurrence |
| Nephritis, Grade 4 | 
 • Treat as grade 3 • On resuming MGC018 reduce dose by two dose levels after first occurrence • Discontinue MGC018 after second occurrence |

ENDOCRINE EVENTS

Endocrine events are a potential risk with MGC018.

Thyroid disorders may occur at any time during treatment with MGC018. Monitor participants for changes in thyroid function per protocol and as indicated based on clinical evaluation and for clinical signs and symptoms of thyroid disorders. Isolated hypothyroidism may generally be managed with replacement therapy without treatment delay and without corticosteroids.

Management guidelines for endocrine events are provided in Table 11.

Table 11. Management Guidelines for Endocrine Events

| Event | Management |
|-----------------------------|---|
| Hyperthyroidism, Grade 1 | 
 • Continue MGC018 • No specific therapy required |
| Hyperthyroidism, Grade 2 | 
 • Hold MGC018 • Consider starting oral corticosteroid therapy. • Short course of corticosteroid such as methylprednisolone 1 to 2 mg/kg IV (or equivalent) divided twice daily. • Resume MGC018 if corticosteroid if corticosteroid dose is reduced to ≤ 10 mg prednisone or equivalent per day and stable on hormone replacement therapy (if necessary). • No dose reduction required after first occurrence • On resuming MGC018, reduce dose by one dose level after second and third occurrences • Discontinue MGC018 after fourth occurrence |
